7.2 Multicenter Studies

Data from all participating sites will be pooled prior to analysis. Listings will include site information as part of the subject ID. The sites will not be considered in any analysis. There is no randomization stratification per site.

7.3 Treatment Descriptors

For table summaries displayed columns will be labelled and ordered:

- CSL312,
- Placebo,
- Total (not applicable for efficacy).

8 Data Handling Conventions

8.1 Missing Data

Missing data occurs when any requested data are not provided, leading to blank fields on the collection instrument. These data will be indicated by the use of a “blank” in subject listing displays. Answers such as “Not applicable” and “Not evaluable” are not considered to be missing data and should be displayed as collected.

Only missing values for the primary efficacy endpoint (i.e., time-normalized number of HAE attacks) during Treatment Period will have an impact on the primary analyses of the comparison between CSL312 versus placebo. The time-normalized number of HAE attacks will be considered as missing for subjects who discontinued within 30 days after the first study drug administration.

The primary efficacy endpoint will be hardly missing due to the robust derivation rule (i.e., the normalization of the number of HAE attacks by time) and treatment policy strategy for the estimand. It is assumed that the outcomes for discontinued subjects are comparable to the outcomes for those who do not discontinue.

In the previous phase II study CSL312_2001 there was no pattern in the attacks under Placebo and CSL312 observed. It can be assumed from study CSL312_2001 that the attack rate for an observation period of > 30 days and < 6 months is comparable to the attack rate of ca. 6 months.

For secondary endpoints which are also based on the HAE attack rate the assumption above is subsequently also applicable.

The details of handling missing data are presented in the corresponding sections of this SAP for respective analyses (e.g., primary and secondary efficacy analyses, safety analyses).

8.1.1 Imputation of Non-Date Missing Data

Subjects with the assessment of treatment relationship for AEs and SAEs missing will have the worst case assumed to impute the relationship: if relationship to study treatment is missing and the event started on or after the first administration of study treatment it will be assumed to be “related”. If the AE or SAE with missing relationship started before the first injection of study treatment (e.g., during Screening Period or Run-in Period), it will be considered as “not related” (realistic case). In listings these imputed relationships will be flagged.

For variables which determine the proportion of events e.g., Adverse Events, all subjects with a non-missing value in the respective analysis set will be included in the denominator when calculating the percentages, unless otherwise stated.

8.1.2 Imputation of Partial Dates

There will be no imputation of partial or complete missing dates.

To determine if an AE is treatment-emergent, see rules in [Section 11.2](#).

To determine the category for medications, see rules in [Section 9.4](#).

8.2 General Derived Variables

8.2.1 Reference Dates and Study Days

Reference dates are used to assign study periods relative to treatment ([Section 8.3](#)).

- The safety reference date is the treatment start date and will be used to calculate study day for safety measures. The respective study day will be calculated as (date of interest - reference date) + 1 if the date of interest occurs on or after the reference date. If the date of interest occurs before the reference date, then the study day will be calculated as (date of interest - reference date). There will be no study day zero.
- The efficacy reference date will be the same as the safety reference date and is the start date of the efficacy evaluation period.

8.2.2 Durations and Time to Event Data

Durations of an event (e.g., duration of an AE) will be calculated in days as:

- (event end date - event start date) + 1.

Thus, there will be no duration of 0. If start and end time are available, they will also be used to calculate the duration in hours or minutes. If start or end date are partially or completely missing duration will not be calculated.

For elapsed time (e.g., onset of AEs) use

- (event date - reference date) or
- event date:time - reference date:time if appropriate.

To transform durations or elapsed times, which are calculated in days into weeks, divide the number of days by 7; to report in months, divide the number of days by 30.4375; to report in years, divide the number of days by 365.25. These algorithms return decimal numbers and ignore the actual numbers of days in the months or years (the calendar days) between start date and stop date. The "year" used in these algorithms is 365.25 days long, and the "month" is one twelfth of that year.

8.2.3 Baseline Definition

Baseline is defined as the most recent, non-missing value prior to first study drug administration. Determination of the baseline value also considers unscheduled visits during the Run-in Period or Screening Period.

All baseline measurements must have been collected prior to the first administration of study drug. Measurements that are obtained after the first study drug administration will be

considered post-baseline values. If the measurement of a variable is not made on a given subject prior to first study drug administration, the baseline value for that subject will be set to missing for that variable.

8.2.4 Change from Baseline

Change from baseline will only be calculated for measures that have non-missing and valid baseline and post-baseline records.

Change from baseline is calculated as:

- visit value – baseline value.

Percentage change from baseline will be calculated as:

- $(\text{change from baseline} / \text{baseline value}) * 100$.

8.2.5 Multiple Assessments

All data will be reported according to the nominal visit date for which it was reported (that is, no visit windows will be applied during data set creation to re-assign assessments to other visits or time points based on such windows).

If a laboratory sample was repeated due to technical problems the results from the valid sample(s) for this visit will be used in the analysis. If a laboratory sample was repeated as safety follow-up to monitor abnormal values of the initial sample, the initial sample (revealing the abnormal values) of this visit will be used in the analysis.

[figure not shown]
Data from all assessments (scheduled and unscheduled), including multiple assessments, will be included in listings.

8.2.6 Actual Treatment

[figure not shown]
Both, planned vial numbers integrated from IRT and the actual administered vial numbers will be collected via eCRF. After general unblinding the subjects' actual treatment will be derived from unblinded vial reports which include all vials with the vial number and actual treatment in those vials. If a subject's actual treatment is the same as the assigned treatment, then actual treatment is the assigned treatment.

If a subject receives a treatment different from the planned it will be decided during the Blinded Data Review Meeting on an individual base what will be considered the actual treatment.

[figure not shown]
CCI

CCI

CCI

CCI

8.2.12 BMI

Body Mass Index (BMI) will be provided via the eCRF and calculated using the following formula:

$$\text{BMI (kg/m}^2\text{)} = \text{Weight (kg)} / [\text{Height (m)}]^2$$

If only one or neither is available, then BMI is missing.

8.3 Study Periods relative to Treatment

The following definitions for the periods of efficacy and safety will be used to define the durations used in the denominator of the time-normalized endpoints and safety endpoints such as exposure and subject-years.

Table 8 Overview Study Periods

Study Period	Start Date	End Date	Duration
Screening Period	date of Informed Consent	date/day on which eligibility for Run-in Period was confirmed	Day 1 Visit date of Run-in Period – date of Informed Consent
Run-in Period	date/day on which eligibility for Run-in Period was confirmed	date of the Day 1 Visit of Treatment Period	Day 1 Visit date of the Treatment Period or Date of Run-in Completion/Non-completion [whichever is first] – Day 1 Visit date of Run-in Period

Study Period	Start Date	End Date	Duration
Treatment Period/ Efficacy Evaluation Period	date of the Day 1 Visit of Treatment Period	date of the Day 182 Visit of the Treatment Period or the End of Study date for subjects who prematurely discontinued [whichever occurs earlier]	Day 182 Visit date of the Treatment Period or End of Study date [whichever is first] – Day 1 Visit date of the Treatment Period + 1
Follow-up Period	date of the Day 182 Visit of the Treatment Period	date of the Follow-up/Final Visit (Day 242 Visit)	date of the Follow-up/Final Visit (Day 242 Visit) – date of the Day 182 Visit of Treatment Period
Safety Period	date and time of the first administration of investigational product	Date of End of Study	Date of End of Study - date of the first administration of investigational product

Technical Notes:

- Screening Period: The first day of the Run-in Period may occur on the same day as the Screening Visit for subjects meeting the eligibility criteria for the Run-in Period. Those subjects will then have no Screening Period.
- Run-in Period: The eCRF ‘Study Completion’ form will only be completed for subjects in the Treatment Period. Thus, if a subject is not eligible for treatment the Run-in Non-Completion is captured on the ‘Treatment Period Inclusion Criteria’ form.
- Follow-up Period: A Follow-up Period will be only available for subjects who did not roll over to CSL312_3002.

9 Study Population

9.1 Subject Disposition

The following summary will be provided by treatment arm and total using the Screened Analysis Set:

- The number and percentage of subjects who provided Informed Consent,
- The number and percentage of subjects screened,
- The number and percentage of subjects who entered the Run-in Period,
 - The number and percentage of subjects who discontinued from the study during the Run-in Period with reason for discontinuation (percentages based on the number who discontinued),
- The number and percentage of subjects who were not assigned to study treatment,
- The number and percentage of subjects who were randomized,

- The number and percentage of subjects who entered the Treatment Period (randomized and received loading dose),
 - The number and percentage of subjects who discontinued the study during the Treatment Period with reason for study discontinuation (percentages based on the number who discontinued),
 - The number and percentage of subjects who prematurely discontinue treatment during Treatment Period with reason for treatment discontinuation (percentages based on the number who discontinued),
 - The number and percentage of subjects who completed the treatment (6-month period with study drug administration once monthly),
- The number and percentage of subjects who completed the study,
- The number and percentage of subjects rolling over to the CSL312_3002 (open-label phase IIIb study),
- The number and percentage of subjects in Screened Analysis Set,
- The number and percentage of subjects in SAF Analysis Set,
- The number and percentage of subjects in ITT Analysis Set,
- The number and percentage of subjects in PP Analysis Set,
- The number and percentage of subjects in PK Analysis Set,
- The number and percentage of subjects in PD Analysis Set.

Technical Note: Subjects will be flagged as completed the study if “Did the subject complete the study?” answered with “Yes” on the EOS form.

Reasons for study withdrawal and study treatment discontinuation will be presented in the order they are displayed in the eCRF.

The following listings will be provided:

- Disposition (date of informed consent, date of eligibility for Run-in, date of randomization, date of first and last study drug administration, End of Treatment (EoT) date, End of Study (EOS) date, reason for treatment discontinuation and/or study discontinuation).
- Analysis Sets (included in Analysis Set: Screened Analysis Set (yes, no), ITT Analysis Set (yes, no), PP Analysis Set (yes, no), PK Analysis Set (yes, no), PD Analysis Set (yes, no), reason excluded from any analysis set).

9.2 Protocol Deviations

All identified protocol deviations throughout the study will be listed prior to database lock and will be classified into minor/major by CSL. Major protocol deviations are defined as deviations that could have a significant effect on the subject's safety, rights, or welfare and/or on the integrity of the study data.

The protocol deviations' classification into minor and major will be reassessed under statistical considerations. During the blinded data review meeting (BDRM), the classification and the subject's assignment to any analysis set will be discussed in detail. The decisions made during the BDRM will be documented in the BDRM minutes and agreed upon prior to database lock for final analysis.

Table 9 Potential Protocol Deviations

Potential Protocol Deviations	Potential Exclusion From Analysis Set
Subject did not provide informed consent and/or informed consent date missing	Screening, SAF, ITT, PP, PK, PD
Subject randomized but not treated with study treatment	SAF, PP, PK, PD
Subjects treated with incorrect study treatment	PP, PK, PD
Subject randomized and treated but does not have at least one measurable PK concentration	PK
Subject randomized and treated but does not have at least one PD measurement	PD
Subject randomized and treated but without primary efficacy assessment	PP
Subject randomized and treated but violated inclusion and/or exclusion criteria	PP, (SAF, ITT, PK, PD)
Subject randomized and treated but compliance outside 80-120%	PP, (PK, PD)
Subject randomized and treated but received prohibited concomitant medication	PP, (PK, PD)
Subject with COVID-19 diagnosis	PP (SAF, PK, PD)

Protocol deviations caused by the COVID-19 pandemic will be documented throughout the entire study. They will be assigned as a separate protocol deviation category "other" with free-text "COVID-19" and discussed during the Blinded Data Review Meeting. COVID-19 related protocol deviations will be summarized and listed separately from all other protocol deviations and will also be discussed in the CSR.

Prior to the Blinded Data Review Meeting, a list of concomitant medications used in the study will be provided to CSL as an Excel file in the same format as the corresponding listing of concomitant medications in the TFL shells. This Excel file will be reviewed by CSL and concomitant medication potentially interfering with the PK/PD analysis or with the efficacy analysis will be flagged. Subjects with such a concomitant medication flagged will be excluded from the respective analysis set.

The following by-subject listings will be provided using the Screened Analysis Set :

- Randomized and actual treatment,
- all protocol deviations related to inclusion and exclusion criteria,
- all protocol deviations leading to exclusion from any analysis set,
- COVID-19 related protocol deviations,
- all other protocol deviations.

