- J: Blood sample for C1-INH functional activity and antigen, and C4 antigen concentration will be collected during the Screening Period for confirmation of historical laboratory values contained in the subject's medical record. If a subject requires the use of on-demand medication to treat an HAE attack within 120 hours (ie, 5 days after C1-INH administration) before Screening, then that subject may return to the study site within the first 2 weeks of the Run-in Period for a second blood draw to assess C1-INH antigen concentration and functional activity, and C4 antigen concentration.
- K: An individual acute treatment plan will be developed by the investigator to ensure that participating subjects are capable of managing their HAE attacks during the study and confirmation of subject's access to on-demand HAE medication to treat HAE attacks. The action plan will be reviewed with subjects.
- L: Repeat remote training is required if 30 days have elapsed between training at the Screening Visit
- M: Refer to [Appendix 2](#) for instructions on HAE attack documentation and assessment.
- N: Access to the eDiary should be closed at the Day 60 Telephone Contact for subjects who are not eligible to enter the Treatment Period. eDiary should be returned.
- O: Berinert is the suggested on-demand medication for use during this study. However, subjects may use the on-demand medication of their choice to treat HAE attacks experienced during the study if that medication has previously been shown to be effective.

Schedule of Assessments: Treatment Period

Study Period	Treatment Period ^A						End of Treatment Period ^{B,C}	Follow-up ^D /Final Visit
	1	2	3	4	5	6		
Month	1	2	3	4	5	6	7	9
Visit Day / Dose Number	1/1	31/2	61/3	91/4	121/5	151/6	182	242
Visit Window (Days)	NA	±4d	±4d	±4d	±4d	±4d	±4d	-14d
Study center visit	X	X	X	X	X	X	X	
Confirm eligibility for Treatment Period ^E	X							
IRT treatment arm assignment	X							
Pregnancy test (at study site) ^{F,H}	X	X	X	X	X	X	X	
Physical examination ^{G,H} , vital signs, and body weight ^H	X	X	X	X	X	X	X	
12-lead ECG ^I	X						X	
Urine collection for urinalysis (central lab)	X ^J			X			X	
Blood Draws (central lab) ^{H,P}	Hematology/Biochemistry / Coagulation		X ^J		X			X
	Retention sample for HAE biomarkers (adults only) ^K		X	X	X	X	X	X
	PK / PD ^L		X	X	X	X	X	X
	Immunogenicity ^M		X		X		X	
Concomitant medications and therapies	↔↔↔↔↔↔↔↔							
Adverse events	↔↔↔↔↔↔↔↔							
PRO / eCOA tablet training ^N	X							

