1.1.3 Background of Disease

Heredity angioedema is a rare genetic disorder classified into 3 disease types [Rosen et al, 1965; Bork et al, 2000], including HAE type 1, HAE type 2, and HAE with normal C1-esterase inhibitor (nC1-INH).

Hereditary angioedema type 1 and type 2 are caused by mutations of the SERPING1 gene, and are characterized by a quantitative decrease in C1-esterase inhibitor (C1-INH) plasma concentrations (type 1) and dysfunctional C1-INH present in normal plasma concentrations (type 2) [Zuraw et al, 2010; Cicardi et al, 2014]. Together, HAE type 1 and type 2 are grouped as HAE with C1-INH deficiency (C1-INH HAE).

A large number of different SERPING1 mutations have been associated with HAE type 1, including missense, nonsense, frameshift, deletion, and insertion mutations [Kalmar et al, 2005]. In general, HAE type 1 is caused by mutations in the C1-INH gene that results in either truncated or misfolded proteins that cannot be secreted [Verpy et al, 1995]. In HAE type 1, an impaired synthesis of normal and functionally active C1-INH occurs, causing a reduction in the availability of functionally active C1-INH levels to between 5% and 30% of normal [Rosen et al, 1965]. Approximately 85% of subjects with C1-INH HAE have HAE type 1 [Longhurst and Bork, 2006].

Most SERPING1 mutations associated with HAE type 2 involve residues at or near the active site on the reactive mobile loop of the C1-INH protein that result in a protein that is secreted but is dysfunctional [Wagenaar-Bos and Hack, 2006]. In HAE type 2, normal levels of a functionally impaired C1-INH molecule are synthesized, but the normal form of C1-INH is considerably reduced in the circulation [Rosen et al, 1965]. Approximately 15% of subjects with C1-INH HAE have HAE type 2 [Longhurst and Bork, 2006].

C1-esterase inhibitor is a serine protease inhibitor that regulates the generation of BK by the plasma contact system, and is the major inhibitor of a number of plasma contact system proteases including FXII and kallikrein [Davis et al, 2010]. Excessive BK formation due to pathological activation of the FXII-driven plasma contact system is a consistent finding in acute episodes of HAE [Björkqvist et al, 2013].

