7.2 Permitted Therapies

The following medications and therapies are PERMITTED at any time during the study:

- Prescribed medication(s) required for the management of acute or chronic medical conditions.
- Therapies to treat any AEs the subject experiences during the study, including nonprophylactic aspirin (eg, to treat a headache).

The following on-demand HAE therapies are PERMITTED at any time during the study for the treatment of HAE attacks if that medication has previously been shown to be effective or if used according to the product label or with deviations from the label as directed by a health care provider:

- Plasma-derived or recombinant C1-INH (eg, Berinert, Cinryze®, Ruconest®).
- Firazyr® (icatibant).
- Kalbitor® (ecallantide).

The use of medications (eg, IV C1-INH) for the prevention of HAE attacks prior to any surgical procedure is PERMITTED at any time during the study.

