4.5 Determination of the Sample Size

In total, 60 subjects are planned to be randomized.

Forty subjects with C1-INH HAE type 1 and type 2 completing the 6-month Treatment Period are needed to achieve a power of approximately 90% for a two-sided Wilcoxon Test (alpha of 5%). Subjects will be randomized to the Active Arm or the Placebo Arm with a ratio of 3:2. An attack rate per month of 0.3125 for CSL312-treated subjects and of 1.3 for subjects receiving placebo are assumed. The monthly attack rates of placebo and of CSL312 are assumed to be Poisson distributed.

The sample size calculation is performed with SAS 9.4 using proc power procedure with twosamplewilcoxon test=WMW which performs power analyses for the Wilcoxon-Test for two independent groups, i.e. the CSL312 and the Placebo treatment in Study CSL312_3001. The Wilcoxon Rank Sum test is testing from departure from the null hypothesis and is assessing if there is a location shift between the distributions of the HAE attack rates of the CSL312 and the Placebo treatment. SAS Proc Power procedure uses the O'Brien-Castelloe approach to compute approximate power. Alpha is set to 5% [O'Brien & Castelloe, 2006]. The assumed monthly attack rates of placebo and of CSL312 (i.e. 1.3 and 0.3125 attacks/month, respectively) are used as the two means of the two Poisson distributions. The randomization ratio of 3:2 was implemented by GROUPNS = (24 16) resulting in a total sample size of 40 which is the lowest one reaching 90% power.

It is targeted to randomize approximately 5 adolescents into the treatment period with a randomization ratio of 3:2 (active:placebo).

To allow for sufficient safety data, to increase the likelihood of adolescents entering the study and, to have at least 40 subjects reaching the end of the study, an additional 20 subjects are planned to be randomized.

In case it is not feasible to randomize the targeted number of adolescents, the targeted total sample size will be achieved by randomizing the needed number with adult subjects.

In addition, it is targeted to include 5 Japanese subjects into the total 60 subjects randomized.

Based on Method 1 and Method 2 in the [Basic principles on Global Clinical Trials] the sample size of the Japanese subjects are planned as below. The point estimate of the endpoint in each arm for Japanese population and other regions (for Method 2) are assumed as the same as that for the global population.

Method 1

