6.6 Pharmacodynamic Analysis Set

The PD analysis set comprise subjects in the safety analysis set for whom at least 1 PD measurement was obtained. PD analysis set will be analyzed using the actual treatment received.

7 General Considerations

Datasets will be created according to Clinical Data Interchange Standards Consortium (CDISC) standards. Study data will be provided in Study Data Tabulation Model (SDTM) format. Analysis data will be provided in Analysis Data Model (ADaM) format.

SAS version 9.4 or higher will be used to perform all data analyses and to generate Tables, Figures and Listings (TFLs).

All ICH required data in the database will be presented in data listings.

Depending on the analysis sets, all data from a subject or a subset of data may be excluded from certain analyses as defined in [Section 9.2](#) (e.g., analyses based on the PP Analysis set).

Summaries of continuous variables will be in terms of the number of missing and non-missing observations, mean (with respective 95% confidence interval (CI), if applicable), standard deviation, median, first quartile (Q1), third quartile (Q3), minimum and maximum.

Categorical variables will be summarized using counts and percentages.

Analyses that use other descriptive statistics will be defined and described in the applicable SAP section.

Summary statistics of location parameters (e.g., mean, median, quartiles) will be reported to one more decimal place than the collected data. Summary statistics of variability (e.g., SD) will be reported to one more decimal place than the commensurate location parameter. For example, the mean and median for age will be reported to one decimal place because it is collected in full years. The SD of age will then be reported to 2 decimal places. Descriptive percentages and proportions will be displayed to one decimal place. Percentages and proportions to be tested will be calculated to 4 decimal places. Durations will be display to 1 decimal place.

The by-subject listings will be sorted by the treatment arm, subject number, and then by visit / date and time, or item number (if applicable).

Formatting for dates and times will be:

- Dates only – ddmmmyyyy;
- Times only – hh:mm or hh:mm:ss (as appropriate);
- Dates and times – ddmmmyyyy hh:mm or ddmmmyyyy hh:mm:ss (as appropriate).

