10.1.1 Primary Estimand

The primary interest is to assess the treatment effect of CSL312 during treatment from Day 1 through Day 182 while subjects are allowed to treat HAE attacks with on-demand medications.

The primary estimand in line with the primary interest of the study follows the treatment policy strategy and is described as follows:

- Treatment Condition: monthly treatment of CSL312 or placebo
- Population: the target patient population defined by eligibility criteria and who were randomized (ITT).
- Variable: time-normalized number of HAE attacks per month during treatment from Day 1 through Day 182.

Intercurrent events: The occurrence of an intercurrent event is irrelevant. All observed values will be used regardless of occurrence of any of the following intercurrent events:

- administration of on-demand medication in addition to prophylactic treatment with CSL312,
- Prohibited concomitant medications due or not due to COVID-19 or COVID-19 vaccination,
- non-compliance to treatment due or not due to COVID-19 or COVID-19 vaccination,
- early study discontinuation due or not due to COVID-19.

- Population-level summary: median time-normalized number of HAE attacks per month during treatment from Day 1 through Day 182 by treatment.

If a subject discontinued the study early after being continuously the first 30 days in the treatment period, the observation is terminated by the Early Termination Visit. It is assumed that the attack rate for subjects, who discontinued the study after the 30th study day and before the end of the 6th month, is comparable to the attack rate from subjects who have the entire 6 months treatment period observed. This assumption is based on CSL312_2001 data which showed that the CSL312 treatment effect was maintained over time. Therefore, the primary endpoint will be considered measurable and not missing, ie, the time-normalized number of HAE attacks will be calculated based on the HAE attacks reported until the Early Termination Visit.

In case a subject discontinues study treatment due or not due to COVID-19 but continues participation in the study for more than 30 days beyond the last study drug administration,

the HAE attacks until the last study drug administration plus 30 days will be included in the HAE attack analysis and length of subject treatment in days will be derived as:

[date of last study drug administration – the date of Study Visit Day 1 of the Treatment Period +31].

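### SAP 9.2 drops the whole subject, not the affected samples, from the PK or PD set for a flagged concomitant drug; if on-demand C1-INH is flagged, PD membership depends on attacks

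*SAP*

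**What the plan says.** SAP 9.2 (Protocol Deviations) describes a list of concomitant medications that goes to the sponsor before the blinded data review meeting. On that list, "concomitant medication potentially interfering with the PK/PD analysis or with the efficacy analysis will be flagged". The consequence follows at once: "Subjects with such a concomitant medication flagged will be excluded from the respective analysis set".

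Other text bears on how this rule would work:

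- SAP 6.6 defines the PD set with no medication clause: "The PD analysis set comprise subjects in the safety analysis set for whom at least 1 PD measurement was obtained". SAP 6.5 has none for PK either.
- SAP 7 allows all or part of a subject's data to be left out, and points to 9.2 for the definition. Section 9.2 gives no rule for part of the data.
- SAP Table 9 has one medication row. It covers prohibited drugs only and lists PP as a potential exclusion, with PK and PD in brackets.
- The PD variables in SAP 13.1 are FXII concentration and FXIIa-mediated kallikrein activity, the latter also as a percentage of baseline.
- Protocol 7.2 permits, for attacks at any time, "Plasma-derived or recombinant C1-INH (eg, Berinert, Cinryze®, Ruconest" and others. Protocol 1.1.3 says that C1-INH "is the major inhibitor of a number of plasma contact system proteases including FXII and kallikrein".
- SAP 9.4 records attack treatment from Run-in onward on its own form, but displays it inside the concomitant medication summaries. Protocol Appendix 2 (2.4) sends on-demand drug taken for prodromal symptoms alone to the concomitant medication record.

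**The concern.** A drug given for an attack can disturb the samples drawn soon after it. The rule instead removes every sample from that subject, at all visits.

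C1-INH is a realistic candidate for flagging, because the protocol itself places its action on the measured pathway. If it is flagged, subjects leave the PD set because they had attacks and treated them. Attack frequency is the primary outcome and is expected to differ about fourfold between arms. The PD set would then lean towards subjects with few or no treated attacks, with the heavier loss on placebo. A comparison of kallikrein activity between arms, or a link between PD and response, would be selected on response. In the PK set, which is summarised for CSL312 subjects only, the same rule would favour subjects with few attacks.

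Leaving C1-INH unflagged does not settle the matter. Samples drawn soon after a dose would then stay in, possibly including the Day 1 sample that normally serves as the percent-of-baseline denominator.

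**Working it through.** **Inputs.** From SAP 4.5: monthly rates of 1.3 (placebo) and 0.3125 (CSL312), Poisson, with 24 placebo and 36 CSL312 subjects randomized. Follow-up is Day 1 to Day 182, and a month is 30.4375 days. The share *u* of attacks treated with a flagged drug is not in the documents, so it is varied from 10% to 100%.

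**The plan's own figure.** SAP 4.5 states about 90% power with 24 + 16 subjects at these rates. The O'Brien-Castelloe method that it names gives 90.7%, and a simulation of 8,000 trials gives 91.4%. The next smaller exact 3:2 split (21 + 14) gives 87.2%. The planning rates are therefore read as the SAP intends.

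**Attacks per subject.** 182 / 30.4375 = 5.979 months.

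- Placebo: 1.3 × 5.979 = 7.77 attacks; P(at least one) = 1 − exp(−7.77) = 99.96%.
- CSL312: 0.3125 × 5.979 = 1.87 attacks; P(at least one) = 1 − exp(−1.87) = 84.6%.

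**Subjects kept under subject-level exclusion.** With *m* = 7.77 or 1.87, the expected number kept is n × exp(−m × u). The chance that the placebo arm empties is [1 − exp(−7.77 × u)]^24.

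| Share u | Placebo kept (of 24) | CSL312 kept (of 36) | P(placebo arm empty) |
|---|---|---|---|
| 10% | 11.0 | 29.9 | about 0 |
| 30% | 2.3 | 20.6 | 8.6% |
| 50% | 0.5 | 14.1 | 60.8% |
| 80% | 0.05 | 8.1 | 95.3% |
| 100% | 0.01 | 5.6 | 99.0% |

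**Sensitivity to varying attack rates.** With negative binomial counts (assumed dispersion 0.5 and 1) and every attack flagged, placebo keeps 1.0 and 2.7 of 24, and CSL312 keeps 9.6 and 12.5 of 36.

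**Sensitivity to drug choice.** The table spreads the flagged drug evenly over attacks. Subjects may instead keep to one drug of their choice. If a share *u* of subjects uses a flagged drug for every attack, the number kept is n × [(1 − u) + u × exp(−m)]. At u = 50% this is 24 × (0.5 + 0.5 × 0.0004) = 12.0 on placebo and 36 × (0.5 + 0.5 × 0.154) = 20.8 on CSL312. The arms then differ less (50% versus 58% kept), and the placebo arm would not empty.

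**Run-in.** These figures count Treatment Period attacks only. With no time window, on-demand use in Run-in, where at least 2 attacks are required for entry, could remove further subjects in both arms.

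**Sample-level alternative.** Let every attack be treated with a flagged drug, and omit samples within *w* days after it. The share of samples affected is 1 − exp(−rate × w / 30.4375).

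| Window w (illustrative) | Placebo samples affected | CSL312 samples affected |
|---|---|---|
| 3 days | 12% | 3% |
| 5 days | 19% | 5% |
| 7 days | 26% | 7% |
| 14 days | 45% | 13% |

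At 5 days, a placebo subject keeps on average 6 × (1 − 0.192) = 4.85 of the six post-dose samples through Day 182. Even at 14 days, the chance of losing all six is 0.45^6 = 0.8%.

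**The case against.** The strongest reply is that the harm needs a decision that the SAP does not announce. Nothing says that on-demand drugs will be flagged. Attack treatment sits on a separate form and may not reach the reviewed list. Section 9.2 concerns deviations, Table 9 names only prohibited medication, and assignment to sets is discussed blinded. Icatibant is also permitted, mild attacks may need no on-demand drug, and the share treated with C1-INH is unknown. All of this stands, and it makes the effect conditional. It does not remove the rule, which is worded as mandatory, at subject level, and wider than Table 9. Prodrome-only use should be on the list in any case. Blinding does not help either, since selection on attacks is informative without knowledge of the arm.

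A reader might infer more than the documents support:

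- *That the placebo PD arm will be emptied.* This becomes likely only if about half or more of attacks receive a flagged drug, and only if that use is spread across subjects.
- *That the rule contradicts the ITT estimand.* SAP 10.1.1 keeps data regardless of "Prohibited concomitant medications due or not due to COVID-19 or COVID-19 vaccination", and Table 9 and SAP 7.1 direct such efficacy exclusions to PP. The natural reading for efficacy is therefore PP. Section 9.2 only fails to say so.
- *That the protocol supplies a washout.* Footnote J of the screening schedule speaks of on-demand use "within 120 hours (ie, 5 days after C1-INH administration) before Screening", but this concerns repeat C1-INH and C4 draws, not the kallikrein assay.
- *That ecallantide raises the same problem.* The documents name it as permitted and say nothing of its mechanism.

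Nor do the documents say how strongly, or for how long, a dose of C1-INH changes this assay.

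**Conclusion.** The concern holds in conditional form. SAP 9.2 sets the wrong unit of exclusion for the PK and PD sets and leaves open whether permitted on-demand drugs trigger it. If C1-INH is flagged, membership of the PD set depends on treated attacks, and CSL312 keeps a larger fraction than placebo in every scenario examined. The gap runs from 46% versus 83% kept (11.0 of 24, 29.9 of 36) at a 10% share to almost none versus 15% when every attack is flagged. It is much smaller if flagged use is concentrated in a subset of subjects. These figures rest on the SAP's planning rates, full follow-up and an assumed share.

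The consequence is confined to PD summaries, which are exploratory and descriptive, and to PK summaries of CSL312 subjects. The primary test and the testing hierarchy contain no PD comparison and are not affected. The change should still be made, because a better rule is available at almost no cost.

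**What to change.** Replace the exclusion sentence in SAP 9.2 with a sample-level rule along these lines:

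> PK or PD samples drawn within a pre-specified interval after a listed interfering drug are flagged and omitted from the corresponding summaries. The subject and all other samples remain in the analysis set. If the Day 1 sample is flagged, percent of baseline is not calculated for that subject, but absolute values are kept. For efficacy, a flagged medication can affect the PP set only.

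In addition:

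- Fix and justify the drug list and the interval for each assay before the blinded data review meeting and before unblinding.
- State whether on-demand use, Run-in use and prodrome-only use fall under the review.
- Report omitted samples by arm, and show summaries with and without them.
- Align 9.2 with SAP 6.5, 6.6, 7 and Table 9.

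The cost is wording and one programmed flag. Dates and times of on-demand doses (Protocol Appendix 2, 2.4.1) and of PD samples (SAP 13.1) are already collected. The downside is some missing PD points, more of them on placebo: about 19% versus 5% of samples under the illustrative 5-day window with every attack flagged. Omission therefore still depends on attacks to some extent, which is why both versions of the summaries are needed.
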